LVEF	Left Ventricular Ejection Fraction
LVO	Left Ventricle Opacification
MedDRA	Medical Dictionary for Regulatory Activities
mg	Milligram
MI	Mechanical Index
min	Minute
mL	Milliliter
mmHg	Millimeter of Mercury
MOD	Magnetic Optical Disc
MR	Magnetic Resonance
MRI	Magnetic Resonance Imaging
mSv	Millisievert
NIMP	Non-Investigational Medicinal Product
PI	Package Insert
RBC	Red Blood cell Count (total erythrocyte count)
RCA	Right Coronary Artery
REB	Research Ethics Board
ROW	Rest of the World – countries outside of Americas, the European Union, and Japan.
S	Second
SAE	Serious Adverse Event
SAER	Serious Adverse Event Report
SAP	Statistical Analysis Plan
SF6	Sulfur Hexafluoride
SPC/SmPC	Summary of Product Characteristics
SPECT	Single Photon Emission Computed Tomography
SUSAR	Suspected Unexpected Serious Adverse Reaction
TN	True Negative
TP	True Positive
UCA	Ultrasound Contrast Agent
UE	Unenhanced
UE-DSE	Unenhanced-Dobutamine Stress Echocardiography
UEUS	Unenhanced Ultrasound

US	Ultrasound
USA	United States of America
USP	United States Pharmacopeia
WBC	White Blood Cell Count (total leukocyte count)
WHO	World Health Organization
βHCG	Beta Human Chorionic Gonadotropin
2D	2 Dimensional

1 Title of Study

A Prospective Multicenter Phase III Clinical Evaluation of the Safety and Efficacy of Lumason™/SonoVue® in Subjects Undergoing Pharmacologic Stress Echocardiography with Dobutamine for the Diagnosis of Coronary Artery Disease

2 Protocol Number

This study is being conducted under protocol number: BR1-142.

IND number: 46,958

EudraCT number: 2015-001962-25.

3 Introduction

Stress echocardiography is an established imaging modality for the detection of coronary artery disease (CAD).^{1,2,3,4,5,6,7} The primary indication for conventional stress echocardiography is to indirectly detect angiographically significant ($\geq 50\%$ diameter) stenoses by inducing ischemia or to assess the patient's risk for a cardiac event.^{5,8,9,10} Increasingly stress echo techniques have been shown to offer valuable prognostic information in the risk evaluation of stable chronic CAD.^{5,10,11} Significant studies (> 100 patients) of dobutamine stress echocardiography (DSE) show a range for sensitivity of between 61–95%, while that for specificity ranged from 51–95%¹¹ for the diagnosis of CAD.¹ The detection of CAD with stress echocardiography is based on the observation of contractile dysfunction in any myocardial segment at rest or with stress; therefore, complete visualization of all left ventricular (LV) endocardial borders (EB) is necessary to document or exclude abnormalities of regional myocardial wall thickening confidently.^{12,13} Interpretation of wall thickening is qualitative, highly dependent on the skill and experience of the reviewing physician, and is affected considerably by quality of endocardial border delineation (EBD).^{12,13} Numerous patient factors may produce suboptimal images with poor EBD. Given, in addition, the challenges imposed by excessive cardiac motion due to hyperventilation and tachycardia at peak stress, non-diagnostic or poor-quality images may occur in up to 30% of patients.^{12,13} The advent of digital side-by-side analysis, standardized reporting criteria, and generalized use of tissue harmonic imaging has reduced, but not overcome, this problem.¹²

Use of ultrasound contrast agents (UCAs) has shown to improve EBD during stress echocardiography and is recommended for use in patients with poor unenhanced image quality by both the American Society of Echocardiography (ASE) and the European Association of Echocardiography (EAE).^{12,13} However, while Lumason™ (sulfur hexafluoride lipid-type A microspheres) with an approved trade name in the USA/SonoVue® (sulfur hexafluoride microbubbles) with an approved trade name for everywhere else in the world referred to hereafter as LUMASON, is approved for use in echocardiography both at rest and stress in the

European Union (EU) and Canada, no UCA is currently approved in the United States of America (USA) for use in stress echocardiography to improve LV EBD in patients with suboptimal unenhanced imaging.

Although generalized use of tissue harmonic imaging has improved image quality, interpretation of stress echocardiograms may still be limited in patients with poor acoustic windows.^{12,14} Recent studies indicate that contrast-enhanced 2 dimensional (2D) echocardiography with harmonic imaging had excellent correlation with radionuclide, magnetic resonance (MR) and computed tomographic (CT) measurements of LV volumes and left ventricular ejection fraction (LVEF) with improved inter-observer agreement and physician interpretation confidence compared to unenhanced harmonic imaging in adult population.^{15,16} Increasing accuracy of LVEF measurements have been associated with contrast-enhanced harmonic imaging over unenhanced harmonic imaging and fundamental imaging, respectively.^{17,18}

Non-diagnostic or poor-quality images may occur in up to 30% of patients during stress because of challenges imposed by excessive cardiac motion due to hyperventilation and tachycardia at peak stress. There are documented benefits through published data regarding the value of the use of contrast agents in stress echocardiography with respect to improvement in image quality and EBD, which further translates into enhanced interpretation of regional and global function with decreased inter- and intra-observer variability.^{4,12} Previous investigations have demonstrated that improving the quality of stress echocardiography images, using contrast agents enables superior visualization of EBD at rest and peak stress across a range of unenhanced baseline image quality (i.e., greatest improvement is seen in patients with the poorest baseline images) with completeness of wall-segment visualization, at both rest and peak stress.^{6,19} The ASE¹ and American College of Cardiology (ACC)²⁰ recommendations for use of contrast enhancement in stress testing have been supported by peer reviewed publications where the importance of adequate visualization of segments for accurate diagnosis have been emphasized.^{1,4,6,19,20}

Due to the increased routine use of DSE as a non-invasive cardiac imaging tool in adults with suspected or known CAD for the detection and/or evaluation of CAD and an increasing number of suboptimal, non-diagnostic quality images mostly with respect to the challenges imposed by excessive cardiac motion due to hyperventilation and tachycardia at peak stress, we aim to study the safety and efficacy of LUMASON-enhanced stress echocardiography with dobutamine in subjects with suboptimal LV EBD at unenhanced echocardiography. This study is being conducted as part of the Phase III program in support of a supplemental New Drug Application (sNDA) to be filed with the Food and Drug Administration (FDA).

4 Study Objectives

Primary Objectives:

- To assess the efficacy of LUMASON-enhanced dobutamine stress echocardiography (DSE) in subjects with suspected or known CAD having suboptimal left ventricular (LV) endocardial border delineation (EBD) at unenhanced echocardiography in terms of:

- Sensitivity and specificity for the detection or exclusion of CAD in unenhanced versus LUMASON-enhanced DSE using coronary angiography or clinical follow-up as the truth standard;
- Critical shift from suboptimal (≥ 2 adjacent segments inadequate on any apical view) at unenhanced dobutamine stress echocardiography (UE-DSE) to adequate images (reduction of suboptimal adjacent segments) for LV EBD at contrast-enhanced dobutamine stress echocardiography (CE-DSE).

Secondary Objectives:

- Change from peak stress non-contrast ultrasound (UE-DSE) versus peak stress contrast-enhanced ultrasound (CE-DSE) in total LV EBD score.
- To obtain safety data in subjects undergoing DSE with LUMASON.

5 Investigational Plan

5.1 Overall Study Design Description

This is a Phase III, prospective, multicenter, within-patient comparison of UE-DSE and CE-DSE that will be conducted at 10-15 sites in subjects with a suboptimal LV EBD on non-contrast 2D transthoracic echocardiography with harmonic imaging at rest and that are scheduled for coronary angiography. Suboptimal LV EBD is defined as published in guidelines, having ≥ 2 adjacent segments on any apical view that are suboptimal^{1,12} during the rest non-contrast ultrasound examination.

Imaging conditions will be representative of those used in routine clinical practice and will include LV EBD, and LV wall motion using harmonic imaging modality with commercially available equipment.

Subjects who are enrolled in the study will undergo a rest non-contrast echocardiogram (UEUS) with the standard apical 4-, 2-, and 3-chamber views obtained with harmonic imaging. A 2 mL dose of LUMASON will be administered as an intravenous bolus injection during rest contrast enhanced echocardiography (CEUS). A recording of 2D transthoracic harmonic echocardiography images will be performed for both UEUS and CEUS rest imaging. At least 30 minutes after the completion of the rest unenhanced echocardiography (UEUS) and contrast enhanced-echocardiography (CEUS) the dobutamine infusion will begin. Once peak stress is achieved (with or without the addition of atropine), subjects will undergo unenhanced dobutamine stress echocardiography (UE-DSE). This will be followed by the contrast-enhanced dobutamine stress echocardiography (CE-DSE) with the administration of 2 mL of LUMASON. A recording of 2D transthoracic images will be performed for both UE-DSE and CE-DSE imaging. The on-site Investigators will provide an overall diagnosis of CAD for each subject from the unenhanced (UEUS and UE-DSE) and contrast-enhanced (CEUS and CE-DSE) echocardiographic images.

The truth standard in this study will be coronary angiography. If coronary angiography is not performed or is indeterminate subjects will be followed for up to 6 months to collect cardiac events.

An off-site assessment of the echocardiographic images will be performed by 3 blinded readers unaffiliated with any of the investigational sites, blinded to the subject's clinical information. The efficacy analysis will be based on the blinded reader evaluations of LV EBD, wall motion abnormalities and diagnosis of CAD.

A fourth blinded reader will assess the coronary angiography images and provide a diagnosis of CAD. The fourth reader will be blinded to the specifics of the protocol including the patient population and the results of the ultrasound examination, but will receive clinical information such as the medical history on the subject.

Safety will be evaluated in this study by the collection of concomitant medications and the monitoring of adverse events, vital signs, electrocardiograms (discrete & continuous), laboratory tests and continuous pulse oximetry.

This study is planned to be conducted in the United States, Canada and Europe.

5.2 Discussion of Study Design

The use of UCAs has shown to improve EBD during stress echocardiography and is recommended for use in patients with poor unenhanced image quality by both the ASE and the EAE.^{12,13,21} However, while LUMASON (under the trade name SonoVue) is approved for use in echocardiography both at rest and stress in the EU, no UCA is currently approved in the USA for use in stress echocardiography to improve LV EBD in patients with suboptimal unenhanced imaging.

The mechanism of action of LUMASON during stress echocardiography would be exactly the same as during an exam at rest. LUMASON would be used in subjects with suboptimal images to enhance the LV cavity and improve the detection of the EB. This Phase III study will, therefore, be conducted with a consistent design (dose, study population and endpoints of both LV EBD score and Sensitivity/Specificity for detection of CAD) based on the Phase III studies previously conducted to obtain approval for the use of LUMASON in echocardiography at rest^{22,23,24} and a previous large, multicenter, dose-ranging study of LUMASON in stress echocardiography²⁵.

The study is designed to assess the safety and efficacy of LUMASON at improving the visualization of the LV EBD during pharmacologic stress echocardiography examinations and for detection or exclusion of CAD.

The study population will consist of adult subjects referred for pharmacologic stress echocardiography and with suboptimal image quality during unenhanced ultrasound imaging at rest who have known or suspected CAD. Subjects to be enrolled in the current study are representative of subjects who could benefit most from CEUS stress echocardiography.

Imaging conditions will be representative of those used in routine clinical practice and will include LV EBD using harmonic imaging modality. Each subject will undergo an unenhanced

echocardiogram (UEUS) followed by a LUMASON-enhanced echocardiogram (CEUS) both at rest. The same applies to the stress echocardiogram when echocardiographic images will be obtained immediately after dobutamine administration (UE-DSE) and then LUMASON will be administered and LUMASON-enhanced stress images (CE-DSE) will be captured. Thus, each subject will serve as its own control and is designed as an intra-patient controlled study.

The current guidelines of American Heart Association (AHA)²⁶ and ASE¹² while they suggest ultrasound contrast use in difficult to image patients with suboptimal image quality at their presenting rest echocardiography exams, their definition of a suboptimal study is when 2 contiguous segments are not visualized in any of the standard 3 apical views. The same criteria will be applied in adults during peak stress imaging, representative of those used in routine clinical practice and will include assessment of LV EBD using harmonic imaging modality.

Taking into consideration the clinical importance, both the diagnostic performance and the LV EBD visualization are defined as co-primary efficacy endpoints for the study.

- First co-primary efficacy endpoint is a comparison of diagnostic performance (sensitivity and specificity) for the detection or exclusion of CAD in unenhanced (UE-DSE) versus Lumason-enhanced DSE (CE-DSE) using coronary angiography or clinical events based on 6 month follow-up as the truth standard. Subjects will be considered to have positive CAD if they have at least one vessel with stenosis $\geq 50\%$ based on the assessment of off-site reader for coronary angiography or have one of the clinical events (cardiac death, non-fatal myocardial infarction, revascularization and need for revascularization) within the 6 month follow-up.
- Second co-primary efficacy endpoint is critical shift from suboptimal (≥ 2 adjacent segments inadequate on any apical view) at unenhanced dobutamine stress echocardiography (UE-DSE) to adequate images (reduction of suboptimal adjacent segments) for LV EBD at contrast-enhanced dobutamine stress echocardiography (CE-DSE).

The secondary efficacy endpoint of LUMASON studies (change from baseline in total of LV EBD score) is the same endpoint for adult studies for LV EBD indication at rest echo examinations.

The muscle and cavity of the LV will be divided into 17 segments (17-segment model). The 17-segment model will be utilized as recommended by the ASE guidelines.^{1,12,27} The standard views of a 2D echocardiogram as defined by the ASE are all used as part of a 2D echocardiogram at rest and stress.²⁶ The clinical utility of improvement in LV EBD resulting from opacification of the LV as an aid in determination of more clinically relevant parameters is recognized by the 2008 ASE consensus statement as leading to improvement in feasibility, accuracy, and reproducibility of echocardiography for the qualitative and quantitative assessment of LV structure and function.¹²

Unevaluable image are defined as images with inadequate visualization of segments comprising all coronary artery territories due to 1 or more of the following artifacts: motion artifacts, lateral wall drop out, swirling or attenuation artifacts. From the published literature⁶ and previous Bracco-sponsored study²⁵ 8% of the UE-DSE images are expected to be unevaluable.

Stress can be induced by either physical exercise or pharmacologic agents. Physical stress was the first reported and used form of stress echocardiography, but it has several disadvantages since during exercise it is not possible to perform close echocardiographic monitoring and recordings are not reliable because of hyperventilation. Pharmacologic stress overcomes these disadvantages.

The pharmacologic stress agent used in this study will be dobutamine. Dobutamine is a direct-acting inotropic agent whose primary activity results from stimulation of the beta-adrenoreceptors of the heart while producing comparatively mild chronotropic, hypertensive, arrhythmogenic, and vasodilative effects. Dobutamine acts primarily on beta-1 adrenergic receptors, with little effect on beta-2 or alpha receptors. In the USA, dobutamine is indicated when parenteral therapy is necessary for inotropic support in the short-term treatment of patients with cardiac decompensation due to depressed contractility resulting either from organic heart disease or from cardiac surgical procedures. In the EU and other countries, dobutamine is also indicated for use in stress echocardiography as an alternative to exercise in patients for whom routine exercise cannot be satisfactorily performed. Even if not approved for use in stress echocardiography in the USA, dobutamine is recommended as the pharmacologic stressor of choice for stress echocardiography by the ACC Foundation Appropriateness²⁰ Criteria Task Force, the ASE, and the AHA.^{1,26} Dobutamine became the preferred stressor in USA as the AHA/ACC guidelines stated that “dobutamine stress echo has higher sensitivity than vasodilator stress echo for detection of CAD.”^{28,29} The recent 2007 recommendations on stress echocardiography of the ASE conclude that “although vasodilators may have advantages for assessment of myocardial perfusion, dobutamine is preferred when the test is based on assessment of regional wall motion.”¹

Based on the Phase III studies conducted to obtain approval for use of LUMASON in echocardiography at rest^{22,23,24} and a previous large, multicenter, dose-ranging study of LUMASON in stress echocardiography²⁵ the proposed dose of LUMASON is 2 mL bolus injection during the rest examination, and then again as a single 2 mL bolus injection after administration of the stress agent, dobutamine, and the UEUS stress examination is completed. There will be at least a 30 minute period between rest and stress LUMASON injections.

The off-site assessments of echocardiographic images will be performed by experienced cardiologists, unaffiliated with the enrolment centers and blinded to the subject’s clinical information. Blinded off-site assessments are used to evaluate diagnostic agents in order to eliminate the potential bias associated with on-site assessments due to the investigator’s knowledge of the subject’s medical history, clinical findings from other modalities, or other clinical information. Thus, the off-site assessments allow for a blinded evaluation of efficacy which is not possible for the on-site assessments.

All subjects will have a truth standard of either coronary angiography or, if coronary angiography is indeterminate or not performed, they will be followed for up to 6 months to collect cardiac events. Although we will study the sensitivity and specificity in detecting anatomic stenoses $\geq 50\%$ in severity, not all the subjects will undergo coronary angiography. Therefore, subjects who do not undergo coronary angiography in the study will be followed for cardiac events (cardiac death, non-fatal myocardial infarction, revascularization and need for

revascularization) at 6 months. The proposed cardiac events as hard end points in the study are widely used, well recognized, robust, measurements of a non-invasive test to predict cardiac events.^{5,7,10}

The coronary angiography images will be reviewed by a single, off-site reader who is an experienced cardiologist to provide a centralized reading for the confirmation of the diagnosis of CAD. He/she will be blinded to the results of the stress echo examination. Medical historical information will be provided to the reader. This will allow the gold standard to achieve the maximum accuracy and reliability. It will also serve to reduce the variability of readings performed by many different unblinded readers on-site across all study sites.

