5.4.1 Inclusion Criteria

Enroll a subject in this study if the subject meets the following inclusion criteria:

- Provides written Informed Consent and is willing to comply with protocol requirements;
- Is at least 18 years of age;
- Has suspected or known CAD and is scheduled to undergo coronary angiography within 6 months after the LUMASON DSE.
- Has undergone a previous echocardiography prior to enrollment; resulting in suboptimal unenhanced images at rest, defined as ≥ 2 suboptimal adjacent segments in any apical view.

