8.6 Efficacy Evaluations

8.6.1 On-Site

The on-site Investigators will provide an overall diagnosis of CAD (Section 8.6.3.3) for each subject based on wall motion abnormalities from the results of the unenhanced (UEUS & UE-DSE) and contrast-enhanced (CEUS and CE-DSE) echocardiographic images.

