Subjects requiring 6 month follow up will be monitored by a review of their hospital and clinic records as well as a phone call follow-up at 6 months to collect cardiac events, as defined by the incidence of: a) cardiac death; b) non-fatal myocardial infarction as defined by a greater than two fold serial elevation in serum creatine kinase-myocardial B (CK-MB) fraction levels; c) coronary revascularization; and d) documentation of the need for coronary revascularization. If a coronary angiography is performed during the 6 month follow-up, this will be collected and accepted as the truth standard for the subject. Each site will have study personnel who will be responsible for collecting phone/clinical record or coronary angiography images during the follow up period.

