10.6.1.1 Truth Standard Diagnosis

For subjects with coronary angiography as the truth standard, a subject will be diagnosed by the blinded off-site coronary angiography reader as Positive if percentage diameter stenosis of any of the vessels (RCA, LAD, LCx and LM) is $\geq 50\%$; otherwise, a subject will be considered as Negative.

For the remaining subjects who didn't have coronary angiography as the truth standard, a subject will be Positive if the subject had cardiac death, documented myocardial infarction, documented

revascularization or need for revascularization during follow up; otherwise, the subject will be considered as Negative.

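### Without a usable angiogram, event-free subjects are scored CAD-Negative and site-documented need for revascularization is not shielded from the study DSE; results should also be shown by truth source

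*Combined protocol and SAP*

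**What the plan says.** Section 5.2 states the anatomical target and its limit in one sentence: "Although we will study the sensitivity and specificity in detecting anatomic stenoses" of 50% or more, "not all the subjects will undergo coronary angiography". It continues that "subjects who do not undergo coronary angiography in the study will be followed for cardiac events". The same section defines Positive as a stenosis of at least 50% or a clinical event. Section 10.6.1.1 closes the rule for everyone without angiographic truth: "otherwise, the subject will be considered as Negative".

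Section 8.6.4.2 lists four events: cardiac death, infarction defined by CK-MB, revascularization, and "documentation of the need for coronary revascularization". Site personnel collect them from records and a telephone call. No criterion for need is given, no evidence is excluded, and neither blinding nor adjudication is described for this branch.

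The study is open label (Section 6.3). In Section 8.6.1, "The on-site Investigators will provide an overall diagnosis of CAD" from both the unenhanced and the enhanced images. Blinding of the truth assessment to the echo result is specified only for the angiography reader (Sections 5.2, 8.6.4.1 and 8.6.5).

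Two provisions limit the branch. At entry each subject "is scheduled to undergo coronary angiography within 6 months after the LUMASON DSE" (Section 5.4.1), and "If a coronary angiography is performed during the 6 month follow-up, this will be collected and accepted as the truth standard for the subject" (Section 8.6.4.2). Section 10.6 plans no analysis by truth source.

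**The concern.** The two sources of truth answer different questions. Angiography measures stenosis; the follow-up branch records whether something happened in six months. A subject with a stenosis of 50% or more and no event becomes Negative and is counted in specificity instead of sensitivity. The closing passage of Section 5.2.1 itself separates risk of coronary events from presence of a significant stenosis.

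The need component raises a second issue. A site that has just read an abnormal CE-DSE could document a need for revascularization on that basis. Without a usable angiogram, the index test would then have supplied its own truth-positive. The plan guards the angiography reader against this and leaves the follow-up branch unguarded.

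Both routes feed the first co-primary endpoint, where CE-DSE must beat UE-DSE on sensitivity and specificity with lower confidence limits of at least 50% (Section 10.6.4). If they matter, the pooled figures cannot be read simply as accuracy for stenosis of 50% or more.

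**Working it through.** **The plan's own figures.** Section 10.7 uses a 25-point difference, 40% discordant pairs, two-sided 5% and 80% power, and gives 45 per truth class. Exact power of the uncorrected McNemar chi-square is 79.4% at n = 44 and 80.4% at n = 45, so 45 reproduces. Then 45/0.30 = 150, and 150/0.85 = 177 or 150 × 1.15 = 173, against a stated 175. All of this takes the truth label as free of error.

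**Inputs from Section 10.7.** 150 evaluable subjects, 45 with CAD and 105 without; CE accuracy 65%, hence UE 40%. The paired cells follow: CE alone correct (0.40 + 0.25)/2 = 0.325; UE alone correct (0.40 − 0.25)/2 = 0.075; both correct 0.65 − 0.325 = 0.325; neither 0.275. The same cells are used for subjects with and without CAD.

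**Assumptions not in the documents.** N0 = 15, 30 or 45 subjects without angiographic truth; six-month event rate p = 10% in unverified CAD. The blinded read is taken to agree with the site read that drives any selection.

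**Case A, no selection into the branch.** Mislabelled CAD: m = N0 × 0.30 × (1 − p). Share of Negatives: f = m/(105 + m). A mislabelled subject is read normal 35% of the time by CE and 60% by UE, contributing −25 points instead of +25, so the specificity difference is 25 × (1 − 2f). The expected sensitivity difference stays at 25.

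**Case B, the branch drawn only from CE-normal subjects.** CE-normal subjects number 45 × 0.35 = 15.75 with CAD and 105 × 0.65 = 68.25 without, 84 in all. For N0 = 30:
- Unverified CAD 15.75 × 30/84 = 5.625; mislabelled 5.625 × 0.90 = 5.06; Positives 39.94; Negatives 110.06.
- Sensitivity: CE 29.25/39.94 = 73.24%; UE (18 − 5.06 × 0.075/0.35)/39.94 = 42.35%; difference 30.9.
- Specificity: CE (68.25 + 5.06)/110.06 = 66.61%; UE (42 + 5.06 × 0.275/0.35)/110.06 = 41.77%; difference 24.8.

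| N0 | A: mislabelled | A: Positives | A: specificity diff. | B: mislabelled | B: Positives | B: specificity diff. | B: sensitivity diff. |
|---|---|---|---|---|---|---|---|
| 15 | 4.05 | 40.95 | 23.1 | 2.53 | 42.47 | 24.9 | 27.8 |
| 30 | 8.10 | 36.90 | 21.4 | 5.06 | 39.94 | 24.8 | 30.9 |
| 45 | 12.15 | 32.85 | 19.8 | 7.59 | 37.41 | 24.8 | 34.4 |

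In case A with N0 = 30, event rates of 5% and 30% give 21.2 and 22.2.

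**Need documented on the study DSE.** Take case A's selection. Let g be the share of CE-abnormal subjects in the branch documented as needing revascularization whatever their anatomy, and let e be the event rate. Such a subject is labelled Positive with probability 1 − (1 − e)(1 − g) if CAD is present and g if not. With e = 5% to 20% and g = 25% to 50%:
- 10% unverified: CE sensitivity 66% to 68%, sensitivity difference 25.3 to 25.6, specificity difference 23.9 to 24.9 (23.0 to 23.3 at g = 0).
- 30% unverified: CE sensitivity 69% to 73%, sensitivity difference 25.9 to 27.0, specificity difference 21.8 to 24.8 (19.6 to 20.3 at g = 0).

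**Angiography-only analysis under case B, N0 = 30.** Verified without CAD: 105 − 24.375 = 80.625. CE specificity (68.25 − 24.375)/80.625 = 54%, Wald lower limit 43.5%. UE specificity (42 − 12.1875)/80.625 = 37.0%, difference 17.4. The sensitivity difference is 31.6.

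**The case against.** The composite truth is prespecified and disclosed. The primary objective in Section 4 is detection or exclusion of CAD against angiography or clinical follow-up. A reader might infer that the plan contradicts itself by naming stenosis and scoring events. It does not: Section 5.2 states and justifies both sources. What remains is a weakness of interpretation.

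A reader might also infer that missed disease shrinks the specificity gain and so works against contrast. That needs a branch unrelated to the test result. If a normal CE-DSE is what leads to no angiogram, the missed cases are CE-normal, the specificity difference barely moves, and the sensitivity difference grows in favour of contrast. The documents do not say which applies. Nor do they say that the study DSE guides cancellation. Even in case A, about 109 to 117 Negatives keep normal-approximation McNemar power for specificity at roughly 98%, 96% and 93%, and Sections 5.4 and 10.7 allow further enrolment if Positives fall short. That repairs the count, not the labels.

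The need limb rests on silence. Section 5.2.1 says subjects have most likely already had DSE or SPECT, so other evidence may exist. All of this stands. It limits the claim about size and direction, and leaves both gaps in the text open.

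Finally, Sections 10 and 10.8 refer to an SAP, and no separate SAP text is before us. The absence of an analysis by truth source is therefore established for Section 10.6 only.

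**Conclusion.** The point holds as a limit on interpretation. In the branch without a usable angiogram, Negative means event-free, which does not establish absence of a stenosis of 50% or more. The need component is not protected from dependence on the index test. It would go too far to say that truth in this branch as a whole depends on the DSE: cardiac death and CK-MB-defined infarction do not use it, and an angiogram in the window replaces the event label.

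Size and net direction cannot be fixed from the documents. On the stated assumptions, the specificity difference lies between 19.8 and 24.9 points instead of 25, and the sensitivity difference between 25 and 34.4, before any need labels based on the DSE. At 10% unverified the effect is small without selection. Cases A and B are extremes; because selection would act through the site read and efficacy is judged on the blinded reads, partial selection is more plausible than either.

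It is also tempting to conclude that the accuracy claim should rest on angiographically verified subjects alone. The arithmetic does not support that. With full selection and 30 unverified subjects, CE specificity there falls to 54% with a lower limit of 43.5%, below the plan's 50% criterion, purely through partial verification.

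**What to change.** 1. In Sections 8.6.4.2 and 10.6.1.1, count need for revascularization as a truth-positive event only when it is documented on evidence other than the study echocardiograms. This is a rule for the truth label and does not touch care.
2. In Section 10.6.1, prespecify sensitivity, specificity and the CE−UE difference by truth source (off-site-read angiography versus 6-month follow-up), as a sensitivity analysis beside the pooled primary result and not in its place.
3. Tabulate the on-site DSE result by whether angiography was done, so that any selection into verification is visible.

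The cost is some wording and two sets of tables; the only extra detail is the evidence on which need was documented. There may be a few fewer event-based Positives, the strata will be smaller, and the angiography-only estimate is itself open to partial-verification bias and should be labelled so. The wording should be settled before the blinded reads are analysed, since a split added afterwards would be post hoc.
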